3. AMENDMENTS AND UPDATES

There is no protocol amendment.

4. MILESTONES

Milestone	Planned date
Completion of feasibility assessment.	23 Sep 13
Start of data collection	22 Feb 2014
End of data collection	14 Jul 2016
Study progress report 1	11 Mar 2014, 11 Mar 2015, 11 Mar 2016
Interim report 1	11 Mar 2015, 11 Mar 2016
Registration in the EU PAS register	17 Dec 2013
Final study report	12 Dec 2016

5. RATIONALE AND BACKGROUND

Hemophilia B (congenital factor IX deficiency or Christmas disease) is an X-linked disorder caused by a congenital deficiency of coagulation factor IX clotting activity. Patients with hemophilia B are usually treated by replacing the missing or defective factor IX for treatment or prevention of hemorrhage. Pfizer has initiated a clinical development program to support the approval of BeneFIX for the control and prevention of hemorrhagic episodes and for surgical prophylaxis in patients with hemophilia B. The clinical development program is comprised of 8 completed clinical studies. Four (4) global studies of the BeneFIX development program supported the original licensure. The other 4 studies (3 global studies and 1 conducted in Japan) were conducted after the initial licensure of BeneFIX. In total, 213 patients with hemophilia B

have received BeneFIX in these studies. Overall, the results of the clinical development program demonstrate that BeneFIX is an efficacious treatment that provides clinical benefit and has an acceptable safety profile in patients with hemophilia B.

In 2007, BeneFIX was reformulated to decrease the occurrence of red blood cell (RBC) agglutination in the syringe or tubing. The reformulation involved no changes to the active ingredient (recombinant FIX protein), but included a change in the diluent (from sterile water to 0.234% sodium chloride [NaCl]). The active recombinant Factor IX in reformulated nonacog alfa is identical to that in original nonacog alfa.

BeneFIX received the first regulatory approval on 11 February 1997 in the United States. Presently it is approved in 67 countries and marketed in 43 countries. Reformulated nonacog alfa was approved for use in the EU in July 2007 and since January 2011 only the reformulated version of nonacog alfa is being distributed, worldwide.

It is estimated that 8,288 patients have been exposed to nonacog alfa since the product was first approved.

BeneFIX has the important advantage over plasma-derived FIX concentrates of being free from the risk of containing blood-borne pathogens because it is not derived from human or animal proteins.

All patients, including previously treated patients (PTPs), minimally treated patients (MTPs) and newborns, infants and very young children, who may present as previously untreated patients (PUPs), with hemophilia B may require FIX replacement treatments for various bleeding events, preventive infusions or a prophylaxis regimen. It is well-known that young children, especially those naïve to FIX, are at greater risk for developing neutralizing antibodies (inhibitors). In addition, they may have altered responses to replacement therapy compared with older hemophilia B patients. While factors such as clinical severity, genetic mutations, exposure intensity and inherent immunoresponse heterogeneity may be risk factors for inhibitor safety issues, it is also important to ensure that these are not specifically related to different FIX replacement products.

Since the introduction of BeneFIX in the United States and in the EU, there have been a total of 136 reports of possible systemic allergic reactions. There have been 56 reports of inhibitor formation.

To evaluate the safety and efficacy of BeneFIX in the usual treatment of hemophilia B in China, a prospective Registry of all severities of patients that are being treated or scheduled to be treated with BeneFIX will be conducted. All Chinese patients of all severities who begin or have begun treatment with BeneFIX for hemophilia B will be eligible for the Registry. These patients must consent to the review and release of their medical records from the time of initiation of BeneFIX therapy through to their conclusion of participation in the study.

The most recent version of the BeneFIX investigator's brochure (IB) provides a summary of findings from clinical studies that are relevant to this registry. Additionally, this document also provides a summary of the known and potential risks and benefits, if any, to human patients.

6. RESEARCH QUESTION AND OBJECTIVES

The registry is to evaluate the safety and efficacy of BeneFIX in hemophilia B patients in the Chinese population.

Primary study objective is to evaluate the product medically important events (FIX inhibitor development, FIX hypersensitivity allergic reaction, thrombogenicity, lack of effect and red blood cell (RBC) agglutination) in Chinese hemophilia B patients during treatment with BeneFIX.

Secondary study objective is to evaluate the overall safety of BeneFIX, including the occurrence of serious adverse events (SAEs) and efficacy

7. RESEARCH METHODS

7.1. Study design

This is a non-interventional, voluntary prospective registry study conducted in major hemophilia treatment centers in China. The registry will enroll Chinese patients with Hemophilia B of all severities. Patients will undergo a screening review prior to enrollment. Enrolled subjects will be treated with intravenous infusions of BeneFIX at a dose and frequency prescribed by the subject's treating physician in accordance with the BeneFIX label and will be adjusted solely according to medical and therapeutic necessity. The registry study will capture observations that will be used for evaluating recombinant FIX replacement product safety, including: subject demographics, medical history, hemophilia history and medications. Safety assessments, treatment data and any laboratory-based FIX inhibitor determinations will be collected at all visits. It is recommended that all subjects in this registry study will be followed for a minimum of 6 months and participation in this registry study will conclude after 12 months.

7.2. Setting

7.2.1 Registry study population

The subject/parent/legal representative and physician's decision to use BeneFIX must be independent of registry participation and determined prior to discussions regarding the registry and obtaining informed consent for participation.

This registry plans to enroll any patient with Hemophilia B in China who is eligible and willing to participate in the registry. Subject enrollment at given centers may vary based on the capabilities of each center. Subjects withdrawn from the registry will not be replaced, regardless of the reason for withdrawal. The registry will be open to enrollment from Registry start date until July 2015.

7.2.2 Approximate Duration of Subject Participation

The frequency of the registry study visits may be conducted following the local standard of care, however, the sponsor recommends that registry study visits be conducted at a minimum of 6 months after the enrollment baseline visit (Day 0) with an additional visit at 12 months after Day 0. A Follow-up Call is to be conducted at least 28 calendar (+10 days) after the Final/Early Termination visit in order to collect information on the occurrence of adverse events and concomitant medications.

7.2.3 Inclusion criteria

Patients must meet all of the following inclusion criteria to be eligible for inclusion in the study:

1. Male subjects of all ages and severity with Hemophilia B.
2. Subjects using or intending to use BeneFIX for Factor IX replacement therapy.
3. Subjects/parents/legal representatives must be able to comply with registry procedures (informed consent/assent process, clinical visits, reporting of infusion and bleed data, reporting of adverse events, etc).
4. Evidence of a personally signed and dated informed consent document indicating that the patient (or a legally acceptable representative) has been informed of all pertinent aspects of the study.

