7.2.4 Exclusion criteria

Patients meeting any of the following criteria will not be included in the registry study:

1. Presence of any bleeding disorder in addition to hemophilia B.
2. Treatment with immunomodulatory therapy (e.g., intravenous immunoglobulin [IVIg], routine systemic corticosteroids, cyclosporins, anti-TNF agents).
3. Treatment with any investigational agent or device within 30 days prior to the Enrollment Visit.
4. Subjects with a past history of, or current factor IX inhibitor. For laboratory-based assessments, any Bethesda inhibitor titer greater than the laboratory's normal range or ≥ 0.6 BU/mL.
5. Known hypersensitivity to hamster protein.
6. Any condition(s) that compromises ability to collect registry-related observations or that poses a contraindication to registry participation (these conditions include, but are not limited

to, inadequate medical history to assure registry eligibility; expectation of poor compliance in provision of observations for registry-related documentation).

7. Unwilling or unable to follow the terms of the registry study.

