7.4. Variables

7.4.1 Baseline Data Collection (Day 0)

Baseline data including:

- Demographic data
date of birth, height, weight, race and ethnicity

- Medical history
 - Immunization and viral infections (HIV, vaccination hepatitis A/B, hepatitis A/B/C)
- Medication history
 - Concomitant diseases and medications including factor IX and other factor IX-containing blood products
- Hemophilia History
 1. Date of the diagnosis of hemophilia B
 2. Age of first exposure to PCC, FFP or any other coagulation factor products
 3. Disease severity
 4. Genetic mutation (if available)
 5. Inhibitor history
 6. FIX hypersensitivity allergic reactions
 7. Family history of hemophilia and inhibitor
 8. Approximate number of exposure days to Factor IX products (e.g. plasma-derived FIX or BeneFIX) that the patient has experienced.
 9. Treatment [prophylaxis regimen (dose and frequency) or on-demand treatment] at the time of enrollment

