7.8. Data analysis

Detailed methodology for summary and statistical analyses of data collected in this study will be documented in a Statistical Analysis Plan (SAP), which will be dated, filed and maintained by the sponsor. The SAP may modify the plans outlined in the protocol; any major modifications of primary endpoint definitions or their analyses would be reflected in a protocol amendment.

A statistical sample size calculation will not be performed for this study. Because all eligible and willing-to-participate subjects will be enrolled in the study and no statistical hypotheses are tested.

All safety and efficacy analyses, except the analysis for Annualized Bleeding Rates (ABR), will be performed on all subjects who receive at least one dose of BeneFIX. ABR analysis will be performed on subjects who participated in prophylaxis period for at least 6 months.

The primary safety outcomes to be reported will be development of clinically significant FIX inhibitors, FIX hypersensitivity allergic reactions, thrombogenicity, lack of effect and red cell agglutination.

Secondary safety outcomes include the frequency of adverse events and serious adverse events, etc.

Secondary efficacy outcomes will be:

- Annualized bleeding rates (ABR) in subjects receiving treatment with BeneFIX,
- The responses to all on-demand treatment with BeneFIX for all bleeds (4 point scale of assessment),
- Number of BeneFIX infusions to treat each new bleed,
- Number of spontaneous/non traumatic breakthrough bleeds within 48 hours of a prophylaxis dose of BeneFIX.

The efficacy results of this study will be presented using descriptive statistics. The following descriptive statistics will be used:

- For numeric endpoints: sample size, mean, standard deviation, median, minimum and maximum;
- For categorical endpoints: count and percentage.

Safety data will be tabulated and listed according to Pfizer's standard reporting algorithms. The reasons for discontinuation of BeneFIX therapy will be described.

Subgroup analysis will be done by several sub-populations.

Additional details of the analysis will be provided in the statistical analysis plan and/or the clinical study report. This information may include details of missing and, if applicable, unused and spurious data. Deviations from the statistical plan will be reported in the clinical study report.

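### Pooling BeneFIX starters with inhibitor-free current users can make the inhibitor percentage understate the risk from the start of BeneFIX, and the baseline form does not record BeneFIX exposure separately

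*Protocol*

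**What the plan says.** **Who enters.** Protocol 7.2.3, criterion 2, admits "Subjects using or intending to use BeneFIX for Factor IX replacement therapy". Section 5 puts it more broadly: "All Chinese patients of all severities who begin or have begun treatment with BeneFIX for hemophilia B will be eligible for the Registry". New and established users are thus eligible on the same terms.

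**Who is kept out.** Protocol 7.2.4, criterion 4, excludes "Subjects with a past history of, or current factor IX inhibitor", with no exception for an inhibitor that arose on BeneFIX. The only hypersensitivity exclusion is criterion 5, "Known hypersensitivity to hamster protein".

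**When counting starts.** Under 9.1.2, adverse event reporting opens with the first dose in the observational period. Under 7.4.3, safety data run from Day 0. Neither refers to the patient's first-ever BeneFIX dose.

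**How it is analysed.** Under 7.8, safety analysis "will be performed on all subjects who receive at least one dose of BeneFIX". The same section says "The primary safety outcomes to be reported will be development of clinically significant FIX inhibitors", followed by allergic reactions, thrombogenicity, lack of effect and red cell agglutination. Subgroups are promised but not named, and the abstract leaves their details to the SAP.

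**What is known about earlier exposure.** Item 8 of the hemophilia history in 7.4.1 asks for "Approximate number of exposure days to Factor IX products (e.g. plasma-derived FIX or BeneFIX) that the patient has experienced". No BeneFIX start date is listed. Section 5 says that patients "must consent to the review and release of their medical records from the time of initiation of BeneFIX therapy".

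**The concern.** Consider two patients who began BeneFIX before the registry opened. The first developed an inhibitor: criterion 4 keeps him out, and his event is never counted. The second did not: he may enrol, and he adds to the denominator. Excluding existing inhibitors is normal when new ones are to be counted. The difficulty arises when that exclusion is combined with current users and the result is reported as one percentage with starters. The established users have already passed through part of their exposure with the outcome of interest filtered out.

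Inhibitor development is the first-named primary outcome. A reader of the final report may take the pooled percentage as the risk a patient faces on starting BeneFIX. For that use it could be too low, and the data listed in 7.4.1 may not be enough to show by how much.

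**Working it through.** The protocol gives no expected incidence, sample size or share of current users, so there is no planned figure to reproduce. Three checks are possible.

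**1. Could there be current users at entry?** Inputs: Chinese approval on 10 July 2012 (abstract), planned start of data collection on 22 February 2014 (Section 4), enrolment open until July 2015 (7.2.1).

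- Approval to start of data collection: 592 days / 30.4375 = 19.4 months.
- Approval to enrolment close: 35.7 months (1 July 2015) to 36.7 months (31 July 2015), so about 36 months.

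Earlier use could therefore span about 19 months for the first patients and about 36 months for the last. These intervals run from approval. No launch date is given, so actual use may have begun later.

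**2. Direction and size for inhibitors.** Let p be the 12-month inhibitor risk in starters, f the share of current users, and r the on-study risk of inhibitor-free current users relative to starters. Then

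pooled risk = (1 - f)p + f·r·p = p × [1 - f(1 - r)].

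The factor is below 1 whenever f > 0 and r < 1. Section 5 supports r < 1 only qualitatively: it describes young children, above all those never exposed to FIX, as at higher inhibitor risk. All values of f, r and p below are assumptions. The table shows pooled risk as a fraction of starters' risk.

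| r | f = 25% | f = 50% | f = 75% | f = 90% |
|---|---|---|---|---|
| 1 | 1.00 | 1.00 | 1.00 | 1.00 |
| 0.5 | 0.875 | 0.75 | 0.625 | 0.55 |
| 0.25 | 0.81 | 0.625 | 0.44 | 0.325 |
| 0 | 0.75 | 0.50 | 0.25 | 0.10 |

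With p = 3% and f = 75%, for example, the pooled figure is 3% × 0.625 = 1.88% at r = 0.5, 3% × 0.4375 = 1.31% at r = 0.25, and 3% × 0.25 = 0.75% at r = 0.

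**3. Could the analysis separate the groups later?** Item 8 merges plasma-derived FIX and BeneFIX into one approximate count. The PUP, MTP and PTP classes in Section 1 are also defined by exposure to FIX products generally. A patient long treated with plasma-derived FIX who takes his first BeneFIX dose on study, and an established BeneFIX user, can therefore have the same item 8 value and fall in the same class. The medication history and item 9 (treatment at enrolment) may give a crude flag for current use. They are not stated to yield a BeneFIX start date or BeneFIX exposure days.

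**The case against.** The strongest reply has four parts.

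- **The target.** The objective in Section 6 concerns events during treatment with BeneFIX, not risk from the first dose. The pooled percentage is a legitimate description of registry participants over their observed time. This stands: the figure is low only relative to risk from BeneFIX start, and the remedy is partly a matter of labelling.
- **The SAP.** Subgroups are deferred to the SAP, which is not at hand and may include a suitable split. This stands for the choice of subgroups. It does not answer the data-collection point, because the SAP cannot reliably build a stratum on BeneFIX exposure if the case report form does not record it.
- **The risk factor.** Section 5 ties higher inhibitor risk to never having had FIX, not to never having had BeneFIX. A BeneFIX starter with long plasma-derived FIX exposure may differ little from a current user, which brings r towards 1. This stands, and is why total prior FIX exposure should be shown beside the BeneFIX split.
- **The other outcomes.** A reader might infer that everyone who had already reacted to BeneFIX is screened out, so that allergic reaction and lack of effect are biased low in the same way. The documents do not support this. No criterion excludes a previous allergic reaction to BeneFIX or previous lack of effect, and 7.4.1 item 6 records allergy history at baseline. Such patients are missing only if they had stopped BeneFIX and did not intend to resume it. That is possible but undocumented.

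It would also go too far to say that new and current users cannot be told apart at all, since the medication history and the records released under Section 5 may help for enrolled patients.

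**Conclusion.** The point holds for FIX inhibitor development. Current users are selected as inhibitor-free, they are pooled with starters, and the pooled percentage understates the risk from BeneFIX start by the factor 1 - f(1 - r) if inhibitor risk falls with exposure. There is no bias if r = 1 or if no current users enrol.

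The size cannot be fixed from the protocol, because neither f nor r is given. Across the assumed values the factor runs from 1.00 down to 0.10. A reader might be tempted to take one cell of the table as the expected bias; nothing in the document supports any particular cell. Nor is 19 months an upper limit on earlier use, because enrolment continues until about 36 months after approval.

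For allergic reaction and lack of effect the mechanism is only a possibility. This does not invalidate the registry. It limits what the pooled inhibitor figure means, and the missing baseline detail is cheap to add.

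**What to change.** - **7.4.1, item 8:** record prior exposure days to BeneFIX separately from those to other FIX products, and add the BeneFIX start date. For enrolled patients, the records released under Section 5 already reach back to that date.
- **7.8:** report inhibitor development by BeneFIX-naive versus BeneFIX-experienced at Day 0, alongside total prior FIX exposure and the pooled figure. Give the other primary events by the same split, descriptively. State that the pooled figure is not the risk from BeneFIX start.
- **Optional:** where screening logs already allow it, give the number of patients excluded for an inhibitor. This should require no new data from people who have not consented.

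The cost is one split field, one date and one stratifier. The downside is smaller strata with less precision. Stratifying does not bring back patients who were excluded or had already stopped, and the screening count would cover only part of that gap. Eligibility need not change.

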7.2.4 Exclusion criteria

Patients meeting any of the following criteria will not be included in the registry study:

1. Presence of any bleeding disorder in addition to hemophilia B.
2. Treatment with immunomodulatory therapy (e.g., intravenous immunoglobulin [IVIg], routine systemic corticosteroids, cyclosporins, anti-TNF agents).
3. Treatment with any investigational agent or device within 30 days prior to the Enrollment Visit.
4. Subjects with a past history of, or current factor IX inhibitor. For laboratory-based assessments, any Bethesda inhibitor titer greater than the laboratory's normal range or ≥ 0.6 BU/mL.
5. Known hypersensitivity to hamster protein.
6. Any condition(s) that compromises ability to collect registry-related observations or that poses a contraindication to registry participation (these conditions include, but are not limited

to, inadequate medical history to assure registry eligibility; expectation of poor compliance in provision of observations for registry-related documentation).

7. Unwilling or unable to follow the terms of the registry study.

7.2.5 Prohibited Concomitant Medication

Treatment with PCC, FFP or any other coagulation products other than BeneFIX is prohibited throughout the registry study unless clinically indicated.

7.3 Study procedures

A written, Pfizer and institutional review board (IRB)/independent ethics committee (IEC)-approved, informed consent/assent (as appropriate) must be obtained before initiating study procedures.

Informed consent must be obtained from the legal representative of the child or adolescent in accordance with local law before assent is sought. An assent should be obtained from all subjects that have an intellectual age of 7 years or more. All potential pediatric subjects should be informed to the fullest and most appropriate extent possible about the study, in language and terms they are able to understand.

If a subject signed assent for a study, a consent must be signed once the subject turns legal age, based on local requirements.

The eligibility of the subject will be evaluated. After inclusion of the subject and after obtaining written informed consent (prior to any registry-related procedure being performed) from the subject's parents/caregiver/legal representative and assent, if applicable, the investigator or site staff will enter the subject data into source documents and into an electronic Case Report Form (eCRF).

Following the baseline data collection (Day 0), the visits to collect registry study data are at the discretion of the investigator and may follow the local usual standard of care, however, the sponsor recommends safety, treatment data and FIX inhibitor assessments at 6 month intervals at a minimum during the 1 year of participation in the registry. A Follow-up Call is to be conducted at least 28 calendar (+10 days) after the Final/Early Termination visit in order to collect information on the occurrence of adverse events and concomitant medications.

